
N/A

e) **Describe alternative procedures or courses of treatment, if any, that might be advantageous to the participant. Describe potential risks and benefits associated with these. Any standard treatment that is being withheld must be disclosed in the consent process and form. (i.e. standard-of-care drug, different interventional procedure, no procedure or treatment, palliative care, other research studies).**

The participants in this study will concurrently receive standard-of-care cognitive-behavioral and pharmacological interventions from the VAPAHCS substance treatment clinics they are enrolled in. There are no potential risks to the participants who receive concurrent cognitive-behavioral and any procedure associated with the proposed research protocol. No participant will be enrolled who is taking a medication that lowers seizure threshold. Risks to confidentiality will be minimized by following all procedures dictated by HIPAA. Of course, potential participants may decline to be involved in the study and receive only the

Title : Transcranial Magnetic Stimulation for the Treatment of Veterans With Alcohol Use Disorders
Approval Period: 02/28/2025 - 02/28/2026

available standard-of-care cognitive-behavioral and pharmacological interventions.

f) Will it be possible to continue the more (most) appropriate therapy for the participant(s) after the conclusion of the study?

This study will not impose any restrictions on treatment/therapy after conclusion. At this point, the rTMS treatment under investigation will only be available during the treatment phase of the study.

g) Study Endpoint. What are the guidelines or end points by which you can evaluate the different treatments (i.e. study drug, device, procedure) during the study? If one proves to be clearly more effective than another (or others) during the course of a study, will the study be terminated before the projected total participant population has been enrolled? When will the study end if no important differences are detected?

In order to have sufficient power to evaluate the primary hypotheses of this study, it is expected to continue until all participants have completed the procedures and follow-up assessments.

3. Background

a) Describe past experimental and/or clinical findings leading to the formulation of the study.

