All data including signed consent form documents must be retained for a minimum of three years past the completion of the research. Additional requirements may be imposed by your funding agency, your department, or other entities. (Policy on Retention of and Access to Research Data, Research Policy Handbook, <http://doeresearch.stanford.edu/policies/research-policy-handbook/conduct-research/retention-and-access-research-data>)

APPROVAL LETTER/NOTICE NOTE: List all items (verbatim) that you want to be included in your approval letter (e.g., Amendment date, Investigator's Brochure version, consent form(s) version(s), advertisement name, etc.) in the box below.

Y By checking this box, I verify that I, as the Protocol Director (PD) responsible for this research protocol, have read and agree to abide by the above obligations, or that I have been delegated authority by the PD to certify that the PD has read and agrees to abide by the above obligations.

Data Analyses

Primary Hypothesis:

1a) Veterans who receive active rTMS treatment for AUD demonstrate a significantly lower frequency of relapse at 6 months following treatment than controls (i.e., Veterans with AUD who receive sham rTMS).

Statistical Approach: Primary Hypothesis 1a will be tested with binary logistic regression. The criterion/dependent measure is relapse status (abstained or relapsed during the 6 months after last rTMS session). Treatment group (active rTMS vs. control) is the target predictor, and covariates will include age and composite neurocognitive functioning (based on demographically adjusted RBANS total score) as these variables may account for both within and between subject group variance [89, 91]. PTSD severity (based on PCL-5 total score), substance use severity (based on NIDA Drug Survey composite score), depression severity (based on BDI total score), and/or smoking severity (based on pack-years) will be considered as covariates if, after random assignment, there are post-hoc differences between treatment groups on these variables following breaking of the blind.

1b) Veterans who receive active rTMS treatment for AUD will demonstrate a significantly greater duration of abstinence in the 6 months following treatment than controls.

Statistical Approach: Primary Hypothesis 1b will be tested with Cox regression. The criterion/dependent measure is duration of abstinence after final rTMS session, and covariates include those listed for Primary Hypothesis 1a.

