Secondary Hypothesis:

In the active rTMS group, Veterans with: (a) lower Glx concentration, (b) lower perfusion (blood flow), and (c) smaller volume of the left DLPFC at baseline will demonstrate a longer duration of abstinence over 6 months post treatment. Confirmation of this hypothesis will indicate that participants who exhibit lower baseline Glx concentration, lower perfusion (blood flow), and/or smaller left DLPFC volume, and receive active rTMS, demonstrate the most robust rTMS treatment response because rTMS addresses these key neurobiological deficits that are associated with increased relapse risk. Confirmation of this hypothesis will advance our understanding of the neurobiological characteristics that predict the greatest benefit from rTMS at entry into treatment for AUD.

Statistical Approach: The Secondary Hypothesis will be tested with generalized linear mixed modeling or linear mixed modeling, depending on the distribution of the dependent measure. Duration of abstinence is the dependent measure. Neuroimaging measure (e.g., Glx level) and treatment group (active rTMS vs. control) are the target predictors, with age as a covariate because it will likely account for significant within and between subject variance [20]. Smoking, PTSD and/or substance use severities will be used as covariates if there are post-hoc differences between treatment groups on these variables after random assignment. We predict an interaction between the specific neuroimaging measure (e.g., Glx level) and treatment group; follow-up simple effect tests will indicate that participants in the active rTMS group with lower Glx concentration, lower perfusion (blood flow), and smaller volume of the left DLPFC at baseline will show the longest duration of abstinence. Separate models will be run for each neuroimaging predictor to minimize the risk of overfitting and corresponding inflated Type I error. To control significance levels of main effects and interactions for multiplicity of tests, we will employ a modified Bonferroni procedure described in our previous studies (see [71] for details).

Exploratory Hypothesis 1

1a) Veterans with co-occurring MDD, who receive active rTMS, demonstrate a significantly lower frequency of relapse over 6 months following treatment than controls (i.e. Veterans with co-occurring MDD who receive sham rTMS).

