Statistical Approach: Exploratory Hypothesis 1a will be tested with binary logistic regression. The criterion/dependent measure is relapse status (abstained or relapsed during the 6 months after last rTMS session). Treatment group (active rTMS vs. control) is the target predictor, with antidepressant use (binary, yes/no) as a covariate. Education and severity of PTSD, substance use, and/or depressive symptomatology will be considered as covariates if, after random assignment, there are post-hoc differences between treatment groups on these variables following breaking of the blind.

1b) Veterans with co-occurring MDD, who receive active rTMS, demonstrate significantly greater duration of abstinence in the 6 months following treatment than controls.

Statistical Approach: Exploratory Hypothesis 1b will be tested with Cox regression. The criterion/dependent measure is duration of abstinence after the final rTMS session. The target predictor and covariates include those for Exploratory Hypothesis 1a.

Exploratory Hypothesis 2

2a) Cigarette smokers, who receive active rTMS, demonstrate a significantly lower frequency of relapse over 6 months following treatment than controls (i.e., Veterans with co-occurring smoking who receive sham rTMS).

Statistical Approach: Exploratory Hypothesis 2a will be tested with binary logistic regression. The criterion/dependent measure is relapse status (abstained or relapsed during the 6 months after last rTMS session). Treatment group (active rTMS vs. control) is the target predictor and with current pharmacotherapy for smoking cessation use (binary, yes/no) as a covariate. Education and severity of PTSD, substance use, and/or smoking severity (based on pack-years) will be considered as covariates if, after random assignment, there are post-hoc differences between treatment groups on these variables following breaking of the blind.

2b) Smokers, who receive active rTMS, demonstrate a significantly greater duration of abstinence over the 6 months following psychosocial treatment than controls.

Statistical Approach: Exploratory Hypothesis 2b will be tested with Cox regression. The criterion/dependent measure is duration of abstinence after final rTMS session. Treatment group is the target predictor and covariates include those for Exploratory Hypothesis 2a.

Tertiary Analyses

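### Four named covariates may join the primary models according to arm differences seen after unblinding, with no threshold; a smaller point is that 1a and 1b are both primary with no success rule

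*Combined protocol and SAP*

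**What the plan says.** Under Data Analyses, Primary Hypothesis 1a, two covariates are unconditional: "covariates will include age and composite neurocognitive functioning (based on demographically adjusted RBANS total score"). Four more are named with their instruments: PTSD severity (PCL-5), substance use severity (NIDA Drug Survey), depression severity (BDI) and smoking severity (pack-years). These "will be considered as covariates if, after random assignment, there are post-hoc differences between treatment groups on these variables following breaking of the blind". Hypothesis 1b takes over the same covariates.

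Similar but not identical clauses follow. For the Secondary Hypothesis, smoking, PTSD and/or substance use "severities will be used as covariates if there are post-hoc differences between treatment groups on these variables after random assignment", with no mention of breaking the blind. For Exploratory Hypothesis 2a the list changes again: "Education and severity of PTSD, substance use, and/or smoking severity (based on pack-years) will be considered as covariates", on the same condition as in 1a. Education is a candidate there but not in the primary models.

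On the primary tests, "Primary Hypothesis 1a will be tested with binary logistic regression" and "Primary Hypothesis 1b will be tested with Cox regression". The heading above them is singular. Section 2g speaks of more than one: "In order to have sufficient power to evaluate the primary hypotheses of this study". Section 2a names the tracking of sobriety as the primary outcome measure, which fits either test. The only multiplicity provision is in the Secondary Hypothesis paragraph, which concerns the neuroimaging models: "To control significance levels of main effects and interactions for multiplicity of tests, we will employ a modified Bonferroni procedure". No alpha, testing order, alpha split or either/both rule is given for 1a and 1b.

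**The concern.** A covariate belongs in the primary model because it predicts relapse. A chance difference between randomised arms says nothing about that. The clause uses such differences as the trigger and defers the judgement until allocation is known. The verb is *considered*, joined to *and/or*, so even an observed difference does not settle whether a variable goes in. Someone who knows the arms can therefore choose the primary model, and a reader of the result cannot tell whether the choice was neutral.

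The second, smaller matter is that the logistic and Cox tests analyse the same six-month relapse data and both carry the primary label. If they disagree, an unwritten rule decides whether the trial succeeded.

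**Working it through.** **Inputs from the documents.** 50 per arm (sections 2a and 8a); two fixed and four conditional covariates (Data Analyses, 1a); relapse of at least 60% within six months (section 1b, stated for a major relapse period, which may not be this trial's endpoint).

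**Assumptions.** Two-sided 0.05 per test; sham relapse of 60%, with 70% and 80% as alternatives; Weibull times with shape 0.7; independent covariates with log-HR 0 or 0.3 per SD (up to 0.5 in step 2); dropout 0 or 20%; HR 0.5 where power is shown. Exceptions are noted. The supplied text gives no alpha, power figure or effect size for 1a or 1b, so there is no plan figure to reproduce.

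**Step 1: how often would something differ by chance?** With four independent candidates and an imbalance threshold p, the chance is 1 - (1 - p)^4.
- p < 0.05: 1 - 0.95^4 = 18.5%
- p < 0.10: 1 - 0.90^4 = 34.4%
- p < 0.20: 1 - 0.80^4 = 59.0%

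The unstated threshold thus decides whether the model departs from age + RBANS in about one trial in five or in more than half.

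**Step 2: the rule applied mechanically.** At 60% relapse, with a t-test threshold of 0.05 or 0.20, simulated type I error is 3.9-5.2%. Power differs from the age + RBANS model by under 1 point at 0.05, and by -1.3 to +2.7 points at 0.20. There is no measurable harm.

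**Step 3: the rule used with discretion.** Four optional covariates give 2^4 = 16 sets. Under the null at 60% relapse, taking the most favourable set gives about 7-9% error for 1a. The figure depends on how prognostic the covariates are. With the four severities correlated at 0.3 and exponential times, it is 6.7%, 10.3% and 12.3% at log-hazard 0, 0.2 and 0.4 per SD.

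**Step 4: what a fixed set costs or gains.** At HR 0.5, 60% relapse and log-HR 0.3 per SD, Cox power is 57.6% with age + RBANS and 66.2% with all six (66.2 - 57.6 = 8.6 points). Logistic power is 54.2% and 59.7% (5.5 points). Across runs at 60% and 80% relapse the gain is about 4-10 points. If the four are not prognostic, little or no power is lost.

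**Step 5: two primary tests** (age + RBANS in both).

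| Sham relapse | Error if either suffices | Exactly one significant at HR 0.5 |
|---|---|---|
| 60% | 6.3-7.3% | 7-14% |
| 70% | 6.9-8.0% | 8-17% |
| 80% | 7.3-7.9% | 9-23% |

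A separate set of runs put disagreement at 6-14%, so the overall range is roughly 6-23%. If both tests are required, error is 2.1-3.7%. Under Holm, error is 3.1-3.8% at 60% relapse, and the chance of any win falls from 59.7% to 48.9% (log-HR 0.3, no dropout, HR 0.5): 59.7 - 48.9 = 10.8 points.

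**The case against.** - **The covariate list is closed.** Four variables are named in advance, each with an instrument, and mechanical use does no harm. Both statements are true. A reader might infer from the clause that it inflates type I error as written; step 2 shows that it does not. What stands is that nothing in the text makes the rule mechanical.
- **The 7-9% figure is a worst case.** It assumes that the most favourable set is sought out. The documents give no sign of that intention, and the inputs are assumed. The figure shows what the wording permits.
- **Differences may not be pure chance.** That holds for everyone randomised. Section 9c withdraws participants with alcohol or substance use during the treatment weeks, the outcome runs from the last session, and no primary analysis set is stated. The objection is fair, but a loose imbalance clause does not repair it.
- **1a and 1b may be two analyses of one outcome.** The singular heading and section 2a allow this reading, but it still does not say which test decides. A reader might also infer an error near 10% from two tests at 0.05 (1 - 0.95^2 = 9.75%). That needs independent tests, whereas these share their data, and the documents never say that either would suffice.
- **The stakes are limited.** Section 3a calls the data preliminary, and section 10a makes roll-out depend on replication and peer review. The documents do not support a reading in which one nominal p-value would settle clinical use.
- **A rule may exist elsewhere.** The grant application is listed as an attachment but was not supplied.

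**Conclusion.** The main point holds: the primary covariate set is left to be chosen after unblinding, on an unsuitable criterion and without a threshold. Its size lies between no measurable harm (mechanical use, 3.9-5.2% error) and about 7-9% error for 1a under the most favourable choice, or up to 12.3% with stronger, correlated covariates. All of this rests on assumed relapse rates, covariate strengths and a two-sided 0.05. The missing success rule is a lesser point. It is worth 1-3 points of error if either test counts, and more in practice when the tests disagree. Both should be fixed. The consequence is moderate, since the trial presents itself as preliminary.

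**What to change.** **Covariates.** Delete the imbalance clause and enter one fixed set in 1a and 1b whatever the imbalance.
- If still blinded: age and RBANS plus those of the four named severities judged prognostic, recorded in writing. All six is acceptable.
- If the blind is already broken: age + RBANS as primary, because it is the only set fixed beforehand, with the all-six model as a sensitivity analysis.
- Label any other adjustment post hoc, and align the Secondary and Exploratory clauses.

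Section 8m places unblinding in year 6, and the Resources section gives an end date of 09/2024. The approval period runs into 2026, but the documents do not say whether the blind has been broken. That must be established first.

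The cost of all six is a few extra parameters in a 100-patient model. If the blind is broken, staying with age + RBANS forgoes the 4-10 points of power that prognostic covariates would bring.

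**Success rule.** Before unblinding, name 1a or 1b as the primary test, with the other tested only after it succeeds or reported as supportive. This gives up the second independent route to success. At HR 0.5 and 60% relapse the chance of any win falls from 59-68% to 49-64% with 1a first, or to 56-65% with 1b first. Part of that loss is the extra error given up. Holm, which needs no order, is an option only if the blind is already broken. It costs about 10 points of power, so it is a real trade-off. If the grant application already states a rule, copy it into Data Analyses.

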The purpose of this study is to evaluate the efficacy of intermittent theta burst (iTBS) transcranial magnetic stimulation (TMS) as a treatment for Veterans with an alcohol use disorder (AUD) to decrease the exceedingly high rate of relapse associated with this condition.

b) State what the Investigator(s) hope to learn from the study. Include an assessment of the importance of this new knowledge.

At least 60% of those with AUD will experience a major relapse period within 6 months of treatment, irrespective of the intervention (psychosocial and/or pharmacological) employed. Consequently, the high prevalence of AUD and relapse following treatment in Veterans is associated with substantial resource allocation and costs for the DVA Health Care System. Current pharmacological and psychosocial interventions demonstrate only a moderate level of efficacy, which is reflected in the high rate of relapse in AUD.

iTBS-TMS is a neurostimulation method that is at the forefront of innovative, non-invasive, and safe treatments for AUD, and the disorders that commonly co-occur with AUD. To reduce the high rate of relapse in Veterans with AUD, it is necessary for interventions to more effectively address the associated neurobiological dysfunction

Title : Transcranial Magnetic Stimulation for the Treatment of Veterans With Alcohol Use Disorders
Approval Period: 02/28/2025 - 02/28/2026

and salient co-occurring conditions. Accordingly, additional rigorously controlled studies are required to determine if iTBS-TMS is an effective treatment for Veterans with AUD.

This double-blind placebo controlled project will deliver completely novel data on the efficacy of iTBS-TMS to promote sustained abstinence for Veterans with AUD during the first 6 months following treatment. Monthly monitoring over the entire first 6 months following treatment is crucial, given relapse within the first 6 months of treatment is robustly related to poor psychosocial functioning over the ensuing 1-3 years. The ultimate goal of this proposal is provide treatment that more effectively promotes sustained abstinence in the Veteran with AUD, as extended abstinence is robustly associated with optimum biomedical, neuropsychological, psychiatric, and psychosocial recovery and functioning.

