Expedited Reporting by the Sponsor to the FDA: PI will review the SAE report to assess completeness of documentation and to determine whether the SAE requires expedited reporting to the FDA. Specifically, if an event meets the criteria for unexpectedness (i.e., not previously reported) and seriousness it will be reported as required by regulation to the FDA within 10 working days for UADEs and within 7 calendar days for unexpected SAEs (Safety Reports) of the sponsor receiving the report as required by regulation.

Data Monitoring Safety Board (DMSB): Reporting of Adverse Events, Adverse Device Effects, Serious Adverse Events, and Unanticipated Adverse Device Effects. Study Personnel will generate tabulations of AEs and SAEs and present a summary of these to the DMSB on a schedule set by the DMSB. The DMSB will also determine when they should be unblinded to treatment assignment for the reviewing of adverse event data. The DMSB will advise the PI concerning whether the study should continue or be stopped for safety

reasons. Communication among the Investigative Team: The PI will have a weekly group lab meeting with all RAs, and there will be a monthly lab meeting with all Co-Is and consultants some via Skype.

Additionally, the VAPAHCs MIRECC has weekly PI meetings to discuss issues relevant to ongoing MIRECC research projects. All key VA Co-Is associated with this project attend these weekly meetings.

d) Explain the point at which the experiment will terminate. If appropriate, include the standards for the termination of the participation of the individual participant Also discuss plans for ensuring necessary medical or professional intervention in the event of adverse effects to the participants.

The experiment will end at either the normal termination or whenever the subject decides to withdraw from the study. Participants will be asked to complete the brief monthly in person or telephone assessments as described in the follow-up phase. In the event that an interim analysis demonstrates futility, the PI, or Co-I determines unacceptable level of risk, regulatory agencies mandate discontinuation of the study, or a product recall occurs that necessitates stopping the study, any planned iTBS-TMS treatments will be immediately discontinued.

e) Data Safety and Monitoring Plan (DSMP). See guidance on Data Safety and Monitoring.

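### The secondary biomarker-by-treatment test models duration of abstinence with a mixed model that has no place for censoring, although the plan uses Cox regression for the same variable elsewhere

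*Combined protocol and SAP*

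**What the plan says.** In Data Analyses, the Secondary Hypothesis predicts that active-arm participants with lower Glx, lower perfusion or smaller volume of the left DLPFC at baseline "will demonstrate a longer duration of abstinence over 6 months post treatment". The test is a biomarker-by-treatment interaction followed by simple effects. There is one model per imaging measure, age is a covariate, and further covariates enter only if the arms differ on them. The model is "generalized linear mixed modeling or linear mixed modeling, depending on the distribution of the dependent measure. Duration of abstinence is the dependent measure". For multiplicity, "we will employ a modified Bonferroni procedure described in our previous studies".

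For the same variable elsewhere the plan says "Primary Hypothesis 1b will be tested with Cox regression" and "Exploratory Hypothesis 1b will be tested with Cox regression. The criterion/dependent measure is duration of abstinence after the final rTMS session". Exploratory 2b does the same.

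On event rates, section 1b says "At least 60% of those with AUD will experience a major relapse period within 6 months of treatment". Section 2a plans monthly contacts, each looking back 30 days.

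On retention, section 9d says "Participants will be asked to complete the brief monthly in person or telephone assessments as described in the follow-up phase". Section 8k pays for completed contacts, and section 9c keeps following people withdrawn after a seizure. No expected dropout rate is stated, and no rule says what duration a lost or withdrawn participant receives.

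**The concern.** Duration of abstinence is, as far as the text shows, one value per person, so a mixed model has nothing for a random effect to describe. It is also a time-to-event variable with a 6-month cut-off. A model of the raw duration treats someone still abstinent at 6 months as if abstinence ended then. Someone lost at month 2 has no defined value at all.

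This hypothesis is meant to show which Veterans gain most from stimulation. An interaction test with 50 per arm is weak to begin with, and weaker after the multiplicity adjustment. A model that loses more power could wrongly dismiss a real predictor. If early loss depends on the biomarker in the active arm, the estimate can shrink, grow or be produced by the loss. The model choice does not touch Primary 1a or 1b, although those analyses also lack a written rule for lost participants.

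**Working it through.** The plan gives no power figure, effect size or numeric alpha for this test, so there is nothing to reproduce. The cost was estimated by simulation.

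**From the documents.** 50 active and 50 sham (section 2a); at least 60% relapse by 6 months (section 1b); a 6-month window and three imaging measures (Data Analyses).

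**Assumed.** Weibull relapse times with shape 0.7; 60% sham relapse by day 182; treatment HR 0.6 at the biomarker mean; biomarker HR 1.8 per SD in the active arm only; standard-normal biomarker; age as a null covariate; two-sided 0.05, with 0.05/3 as the strictest step for three measures. Each scenario has 6,000 trials, so the Monte Carlo SE is at most √(0.5 × 0.5 / 6,000) = 0.65 points.

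**Step 1: censoring at 6 months.** In sham, 1 − 0.60 = 40% are still abstinent. In active, at the biomarker mean, 0.40^0.6 = 58% are.

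**Step 2: base-case power (%).** The linear model is the LMM with one record per person. Each cell gives power at 0.05, then at 0.05/3.

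| Random dropout | Linear, last contact | Linear, lost excluded | Cox |
|---|---|---|---|
| 0% | 37.1 / 21.6 | 37.1 / 21.6 | 51.8 / 35.0 |
| 20% | 30.4 / 17.1 | 35.1 / 20.6 | 50.1 / 33.5 |
| 30% | 27.4 / 15.1 | 33.1 / 18.1 | 48.4 / 32.0 |

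Without loss the gap is 51.8 − 37.1 = 14.7 points. At 30% dropout with last-contact entry it is 48.4 − 27.4 = 21.0 points. A gamma GLM without loss has 36%.

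**Step 3: range without loss.** Over sham relapse of 60–75% and treatment HR of 0.6–1.0, linear power is 37–58% and Cox 52–67%, a gap of 9–15 points. Gamma is 16–17 points below Cox at treatment HR 0.6 but only 1–2 below at HR 1.0. With no true interaction and no loss, rejection is 4.8% linear, 5.3% gamma and 5.8% Cox.

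**Step 4: other shapes (linear v Cox).**
- Interaction only in the first 30 days: 14% v 14%.
- Only in the first 60 days: 21% v 23%.
- Only after day 60: 8.4% v 16.5%.
- Lognormal times: 43% v 57%.

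**Step 5: random loss and the estimate.** With no loss the interaction is −23.0 days per SD. Last-contact entry gives −20.7 at 20% dropout (20.7/23.0 = 0.90) and −19.4 at 30% (0.84). Exclusion gives −24.5 and −25.0.

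**Step 6: loss related to the biomarker in the active arm** (20–30% dropout, logit slope 0.5–1.0 per SD).
- Loss rising as the biomarker falls: −8.9 to −15.8 days with last-contact entry, −20.1 to −22.6 with exclusion. Linear power is 10–30% v Cox 48–50%.
- Loss rising with the biomarker: −24.6 to −28.6 days with last-contact entry, −26.2 to −30.0 with exclusion.
- No true interaction: false positives of 6–12% (last contact), 5–8% (exclusion) and 5–6% (Cox).

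**Step 7: where Cox fails.** If 20/40/60% of relapsers are censored at the last contact before relapse, Cox has 45/37/27% and linear with last-contact entry 39/39/38%. Cox counting loss as relapse keeps 53/54/53%, but gives 8–18% false positives under the loss in step 6.

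**Cross-check.** Separate code with exponential times and a log HR of 0.7 per SD gave Cox 0.74 v linear 0.65 with no main effects, and 0.67 v 0.47 with treatment HR 0.6. With biomarker-related loss and no true interaction, the spurious effect was negative when lost people were entered at last contact, excluded or counted as relapsed at day 0. It was positive when they were counted as abstinent to 6 months. The coding rule therefore sets the direction.

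**The case against.** The strongest reply is that, with complete follow-up, this is a choice of estimand. The linear model then validly estimates mean abstinent days up to 6 months, which suits a hypothesis about longer abstinence, and most scenarios above assume a hazard-ratio interaction that favours Cox. This stands in part: without loss the cost is power and not validity, and for effects confined to the first 30 or 60 days it is 0–2 points.

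Some of the Cox gain may reflect a slightly liberal test. Adjusting for size gave a gap of 13 points in the base case and 5–13 over the range. At 85% sham relapse it was 3–5 points adjusted, while another run gave about 9 unadjusted. A further run of 2,000 trials put null rejection at 5.0% for Cox and 4.7% for linear. The gap narrows but remains.

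The hypothesis is worded within the active arm. For that simple effect the gap is smaller, 2–7 points without loss, but 14–20 with random dropout.

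The plan has retention measures and states no dropout rate, so early loss is an assumption. Cox also loses its advantage when loss hides relapse. Both points stand, and the second is why a sensitivity analysis is needed.

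Finally, a mixed model of monthly data may have been intended, and the grant application, listed as an attachment, may say more. The current text names duration itself as the outcome and defines no repeated measure.

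**Conclusion.** The concern holds and should be fixed. That the model is under-specified and differs from the plan's other analyses of the same variable is plain from the text. The size is less certain because every effect size and dropout rate is assumed. In most scenarios the linear model costs about 9–15 points of power without loss, and more with random dropout, but almost nothing if the interaction acts only early. Bias needs early loss, and its direction depends on who is lost and on a coding rule that the plan does not give. Confidence in the magnitude is medium.

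**What to change.** Replace the model sentence with:

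> The Secondary Hypothesis will be tested with Cox regression of time from final rTMS session to first relapse, censored at last completed contact or 6 months, with terms for treatment, biomarker, treatment × biomarker and age, plus the conditional covariates already listed for this hypothesis; one model per biomarker, interaction first, then simple effects, with the modified Bonferroni procedure.

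- Do not describe it as the Primary 1b model. There, "covariates will include age and composite neurocognitive functioning (based on demographically adjusted RBANS total score".
- Add one sensitivity analysis that counts loss to follow-up as relapse at last contact. Its false-positive rate in step 7 makes it unsuitable as the main test.
- State how participants withdrawn during the treatment phase (section 9c) enter the analysis.
- If an effect in days is wanted, report the linear model as supportive and say how lost people enter it.
- If a repeated monthly outcome was intended, define it and its random effect, for example abstinent days per 30-day window with a participant random intercept, and do not call it duration of abstinence.
- Section 8m places unblinding in year 6 and the study end in September 2024. If the blind is already broken, date and disclose the change and report the model now in the plan beside the new one.

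The cost is SAP wording and one model call, since Cox regression and the monthly contacts are already planned. The result is a hazard ratio and not days. Power stays modest: at biomarker HR 1.8, Cox has 48–67% at 5% and 32–50% at 0.05/3 over the no-loss and random-dropout scenarios, and less for smaller effects.
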